# 7.3. MISSING DATA

Missing data will not be imputed but analyzed as missing, except as specified in Section 14.2.

# 7.4. EXAMINATION OF SUBGROUPS

Additional exploratory stratification will be made for summarizing some of the PK and/or PD endpoints, including:

- Male versus female (PK only)
- CKD1 versus CKD2 (within Cohorts 1 and 3)

Document: PK/PD STATISTICAL ANALYSIS PLAN
Author: [name]

Author: [name] Version Number: 1.0

Version Date: 12 Aug 2019

Template No: CS\_TP\_BS016 - Revision 5 Reference: CS\_WI\_BS005

Effective Date: 01Apr2018

Palladio BiosciencesInsert Customer Name/Logo PK/PD STATISTICAL ANALYSIS PLAN: PROTOCOL PA-102 Page 18 of 39

# 8. OUTPUT PRESENTATIONS

APPENDIX 1 shows the conventions for presentation of data in outputs. The output shells provided with this SAP describe the presentations for this study and therefore the format and content of the summary tables, figures, and listings to be provided by IQVIA Biostatistics. Some minor modifications may be necessary to the planned design of tables, figures, and listings to accommodate data collected during the actual study conduct.

#### 8.1. **TREATMENT SUMMARIZATION**

In general, data will be presented for each cohort, distinguishing between the different renal groups (CKD1/2, CKD1, CKD2, and CKD3) and dosages (50 mg, 200 mg). Data may also be presented for all study subjects combined where appropriate.

#### 8.2. **PRECISION**

All PK concentrations and PD variables will be reported and analyzed with the same precision as the source data provided by the bioanalytical laboratory regardless of how many significant figures or decimal places the data carry. Elapsed time variables for PK or PD will be reported with 2 decimal places with unit of hours. Derived percentages for PD variables (if any) will be reported in listings with 1 decimal place. Derived PK parameters will be rounded for reporting purposes in by-subject listings. The rounded derived PK data will be considered the source data for the calculation of descriptive statistics. For most derived PK parameters, 3 significant figures will be used as the standard rounding procedure for listings, with the following exceptions:

PK/PD STATISTICAL ANALYSIS PLAN Document:

Author: [name] Version Number: 1.0 Version Date: 12 Aug 2019

Template No: CS\_TP\_BS016 - Revision 5 Reference: CS\_WI\_BS005

Effective Date: 01Apr2018

Palladio BiosciencesInsert Customer Name/Logo PK/PD STATISTICAL ANALYSIS PLAN: PROTOCOL PA-102 Page 19 of 39

- Parameters directly derived from source data (e.g., Cmax) will be reported and analyzed with the same precision as the source data.
- Parameters derived from actual elapsed sample collection times (e.g., tmax) will be reported with the same precision as the actual elapsed sampling time value of the source data (specified as 2 decimal places with unit of hours).

For the reporting of descriptive statistics, the mean, geometric mean, median, and SD will be presented to 1 digit more precision than the source data. The minimum and maximum will be presented to the same precision as the source data. Summary percentages (e.g., for categorical variables), CV (%), and geometric CV (%) will always be reported to 1 decimal place.

### 9. DISPOSITION AND WITHDRAWALS

See Non-PK/PD SAP.

#### 9.1. **PROTOCOL DEVIATIONS**

A protocol deviation is defined as an unintended or unanticipated departure from the procedures or processes that were approved by the Sponsor and the Investigational Review Board and agreed to by the Investigator.

Protocol deviations will be documented by the clinical monitor throughout the course of monitoring visits. Investigators will be notified in writing by the monitor of deviations, which will be recorded in the subject's source documentation. This information will be provided to IQVIA Biostatistics to determine inclusion/exclusion from analysis sets.

PK/PD STATISTICAL ANALYSIS PLAN Document:

Author: [name] Version Number: 1.0 Version Date: 12 Aug 2019

Template No: CS\_TP\_BS016 - Revision 5 Reference: CS\_WI\_BS005

Effective Date: 01Apr2018

Palladio BiosciencesInsert Customer Name/Logo PK/PD STATISTICAL ANALYSIS PLAN: PROTOCOL PA-102 Page 20 of 39

#### 9.1.1. **DEVIATIONS RELATED TO STUDY CONDUCT**

Major deviations can include, but may not be limited to:

Deviations related to PK and PD analysis (see Section 9.1.2)

Refer to Non-PK/PD SAP for other examples.

#### 9.1.2. **DEVIATIONS RELATED TO PK AND PD ANALYSIS**

Protocol deviations or events will also be reviewed by the study pharmacokineticist and biostatistician to identify deviations or events which have the potential to affect the PK or PD results. Deviations resulting in no evaluable PK or PD results for a subject, and thus exclusion from PK or PD analysis set, will be documented as reasons for exclusion from these analysis sets.

Changes to the procedures which may impact the quality of the PK or PD data will be considered major protocol deviations and will be described within the CSR body text. Other events which may impact the quality of the PK or PD data will be described within the CSR body text. These changes or events will include any circumstances that will alter the evaluation of the PK or PD. Examples include, but may not be limited to, vomiting following oral dosing occurring within the time frame of 2 times the median tmax (within that cohort, excluding data potentially affected), sample processing errors that lead to inaccurate bioanalytical results, and/or inaccurate dosing for the dosing interval for which PK or PD sampling occurs. In the case of a major protocol deviation or event, PK and/or PD data collected during the relevant time period will be listed but excluded from summaries. Other changes to the procedures or events which do not impact the quality of the PK or PD data will not be considered major protocol deviations. Common examples of minor protocol deviations

PK/PD STATISTICAL ANALYSIS PLAN Document:

Author: [name] Version Number: 1.0 Version Date: 12 Aug 2019

Template No: CS\_TP\_BS016 - Revision 5 Reference: CS\_WI\_BS005

Effective Date: 01Apr2018

Palladio BiosciencesInsert Customer Name/ Logo PK/PD STATISTICAL ANALYSIS PLAN: PROTOCOL PA-102 Page 21 of 39

are a missed sample or minor deviations from sample collection times/windows.

### 10. Demographic and other Baseline Characteristics

See Non-PK/PD SAP.

### 11. SURGICAL AND MEDICAL HISTORY

See Non-PK/PD SAP.

# 12. PRIOR AND CONCOMITANT MEDICATIONS

See Non-PK/PD SAP.

### 13. STUDY MEDICATION EXPOSURE AND COMPLIANCE

See Non-PK/PD SAP.

### 14. PHARMACOKINETIC ANALYSIS

Derivation of the PK parameters from lixivaptan and lixivaptan metabolite (WAY-141624, WAY-138451, and WAY-138758) concentrations will be the responsibility of the clinical pharmacokineticist at IQVIA. The PK and PD summaries, listings, tables, and figures will be the responsibility of the PK/PD biostatistician at IQVIA. Primary PK variables include lixivaptan and lixivaptan metabolite concentrations and parameters.

Document: PK/PD STATISTICAL ANALYSIS PLAN

Author: [name] Version Number: 1.0

Version Date: 12 Aug 2019

Template No: CS\_TP\_BS016 - Revision 5 Reference: CS\_WI\_BS005

Effective Date: 01Apr2018

Palladio BiosciencesInsert Customer Name/Logo PK/PD STATISTICAL ANALYSIS PLAN: PROTOCOL PA-102 Page 22 of 39

### 14.1. PLASMA CONCENTRATION DATA

A listing of PK blood sample collection times as well as derived sampling time deviations will be provided. A subject listing of all concentration-time data will be presented. Presentation of individual sampling times/concentrations will be based on the Safety Analysis Set.

Lixivaptan and lixivaptan metabolite (WAY-141624, WAY-138451, and WAY-138758) plasma concentrations will be tabulated and summarized by analyte, cohort (equivalent to stratification by renal function/CKD stage and dose), Study Day, dosing interval (AM/PM), and nominal time point using descriptive statistics as described in Section 6.1 and Section 8. Additional summarization will be made with further stratification by gender (male versus female), and, independently, by CKD stage within cohort. Plasma concentrations that are below the lower limit of quantification (BLQ) will be treated as zero for the computation of summary statistics. Concentration summaries will be based on the PK Analysis Set.

The following plots will be presented for the concentration-time data:

- Arithmetic mean concentration versus time data (±SD) for Day 1 and Day 7 will be presented on linear and semi-logarithmic scales, stratified by analyte, cohort (equivalent to stratification by renal function/CKD stage and dose; and further stratified by CKD stage within cohort), Study Day, and dosing interval (AM/PM), based on the PK Analysis Set. Additional figure(s) will be made with further stratification by gender (male versus female).
- Arithmetic mean trough concentration versus nominal Study Day data (±SD) will be presented on a linear scale, stratified by analyte, cohort (equivalent to stratification by renal function/CKD stage and dose; and further stratified by CKD stage within cohort), and dosing interval (AM/PM), based on the PK Analysis Set. Additional figure(s) will be

PK/PD STATISTICAL ANALYSIS PLAN Document:

Author: [name] Version Number: 1.0 Version Date: 12 Aug 2019

Template No: CS\_TP\_BS016 - Revision 5 Reference: CS\_WI\_BS005

Effective Date: 01Apr2018

Palladio BiosciencesInsert Customer Name/Logo PK/PD STATISTICAL ANALYSIS PLAN: PROTOCOL PA-102 Page 23 of 39

made with further stratification by gender (male versus female).

Individual subject concentration versus time data will be graphically presented on linear and semi-logarithmic scales, by analyte, cohort (and CKD stage within cohort), Study Day, and dosing interval (AM/PM), based on the Safety Analysis Set.

### 14.2. PHARMACOKINETIC PARAMETERS

Subjects with partial data will be evaluated on a case-by-case basis to determine if sufficient data are available for reliable estimation of PK parameters. Any anomalous concentration values (e.g., quantifiable predose concentration for first dose) observed at predose will be identified in the CSR and used for the computation of PK parameters. For first dose, if the anomalous predose concentration is greater than 5% of Cmax of the profile in that dosing interval, the PK parameters for the given subject/profile will be calculated and reported in the listing but flagged and excluded from statistical summaries and analyses. Predose concentrations will be considered as collected simultaneously with the dose for purpose of PK parameter calculation.

For PK parameter calculations for first dose, predose samples that are missing will be assigned a numerical value of zero. For calculating parameters, no imputation/substitution will be made for missing predose and/or trough concentrations for Day 1 PM or Day 7 AM or PM. For all dosing intervals, any BLQ concentrations (including predose) will be assigned a value of zero if they precede quantifiable samples in the initial portion of the profile. A BLQ value that occurs between quantifiable data points, especially prior to Cmax, will be evaluated to determine if an assigned concentration of zero makes sense, or if exclusion of the data is warranted. Following Cmax, BLQ values embedded between 2 quantifiable data points will be treated as missing when calculating PK parameters. If a BLQ value occurs at the end of the

PK/PD STATISTICAL ANALYSIS PLAN Document:

Author: [name] Version Number: 1.0 Version Date: 12 Aug 2019

Template No: CS\_TP\_BS016 - Revision 5 Reference: CS\_WI\_BS005

Effective Date: 01Apr2018

Palladio BiosciencesInsert Customer Name/ Logo PK/PD STATISTICAL ANALYSIS PLAN: PROTOCOL PA-102 Page 24 of 39

collection interval (after the last quantifiable concentration), it will be set to zero. If consecutive BLQ concentrations are followed by quantifiable concentration(s) in the terminal portion of the concentration curve, these quantified values will be excluded from the PK analysis by setting them to missing, unless otherwise warranted by the concentration-time profile.

The following PK parameters (

Document: PK/PD STATISTICAL ANALYSIS PLAN

Author: [name] Version Number: 1.0

Version Date: 12 Aug 2019

Template No: CS\_TP\_BS016 - Revision 5 Reference: CS\_WI\_BS005

Effective Date: 01Apr2018

Palladio BiosciencesInsert Customer Name/ Logo PK/PD STATISTICAL ANALYSIS PLAN: PROTOCOL PA-102 Page 25 of 39

Table 3) will be estimated for lixivaptan and lixivaptan metabolites by non-compartmental methods using validated software and actual elapsed time from dosing. See Table 5 for specific Study Days and dosing intervals for which each PK parameters will be calculated. A minimum of 3 quantifiable post-dose concentration-time data points will be required for calculation of PK parameters.

Document: PK/PD STATISTICAL ANALYSIS PLAN

Author: [name] Version Number: 1.0
Version Date: 12 Aug 2019

Template No: CS\_TP\_BS016 - Revision 5 Reference: CS\_WI\_BS005

Effective Date: 01Apr2018

Palladio BiosciencesInsert Customer Name/ Logo PK/PD STATISTICAL ANALYSIS PLAN: PROTOCOL PA-102 Page 26 of 39

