### 7.2. ESTIMANDS

As per International Council for Harmonisation E9 (R1), the estimands for this study are described as follows:

Primary Estimand 1: See Non-PK/PD SAP.

Primary Estimand 2: The PK profile of lixivaptan and its major metabolites (WAY-141624, WAY-138451, WAY-138758) following first and multiple doses of lixivaptan in ADPKD subjects.

- Population: ADPKD subjects with at least one post-dose PK assessment and defined further through appropriate inclusion/exclusion criteria.
- Variables (or endpoints): PK concentrations and parameters (Cmax, tmax, AUC from time 0 until the last quantifiable concentration [AUC(0-last)], AUC

Document: PK/PD STATISTICAL ANALYSIS PLAN

Author: [name] Version Number: 1.0

Version Date: 12 Aug 2019

Template No: CS\_TP\_BS016 - Revision 5 Reference: CS\_WI\_BS005

Effective Date: 01Apr2018

Palladio BiosciencesInsert Customer Name/ Logo PK/PD STATISTICAL ANALYSIS PLAN: PROTOCOL PA-102 Page 17 of 39

extrapolated to infinity [AUC(0-inf)], AUC from time 0 until 14 hours post-dose [AUC(0-14)], terminal elimination phase half-life [ $t_{1/2}$ ], apparent terminal elimination rate constant [ $\lambda_Z$ ], apparent systemic clearance after extravascular dosing [CL/F; lixivaptan only], and apparent volume of distribution after extravascular dosing [ $V_Z$ /F; lixivaptan only]).

- Strategy for addressing intercurrent event: Regardless if subject discontinues treatment prematurely.
- Population-level summary: Descriptive differences in PK parameter means of the four cohorts.

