# **Table 3 Estimation of PK Parameters**

Dar	1	A	T.	Æ	
Dav		Α	. 13	/1	:

PK Parameter	Definition
C max	Maximum observed plasma drug concentration (ng/mL), obtained
	directly from the observed concentration versus time data.
t max	Time to reach maximum plasma concentration (h), obtained directly from
	the observed concentration versus time data.
AUC (0-last)	Area under the concentration-time curve from time 0 until the last
	quantifiable concentration (ng·h/mL), calculated by linear up/log down
	trapezoidal summation.
AUC (0-inf)	Area under the concentration-time curve from time 0 extrapolated to
	infinity (ng·h/mL), calculated by linear up/log down trapezoidal
	summation and extrapolated to infinity by addition of the last
	quantifiable observed concentration divided by the elimination rate
	constant: $AUC_{(0-last)} + C_{last}/\lambda_z$ .
$\lambda_{Z}$	Apparent terminal elimination rate constant (1/h), determined by linear
	regression of the terminal points of the log-linear concentration-time
	curve. The Best Fit method utilized by WinNonlin will be used to identify
	the terminal linear phase of the concentration-time profile, with visual
	assessment and adjustment of the selected data points by the PK scientist
	if warranted. A minimum of 3 data points will be used for determination.
t 1/2	Apparent terminal elimination phase half-life (h), determined as $ln2/\lambda_Z$ .
CL/F	Apparent systemic clearance after extravascular dosing (L/h), calculated

Document: PK/PD STATISTICAL ANALYSIS PLAN

Author: [name] Version Number:

1.0 12 Aug 2019

Template No: CS\_TP\_BS016 – Revision 5 Reference: CS\_WI\_BS005

Effective Date: 01Apr2018

 $Copyright © 2009, 2010, 2012, 2016, 2018 \ IQVIA. \ All \ rights \ reserved. \ The \ contents \ of \ this \ document \ are \ confidential \ and \ proprietary \ to \ IQVIA \ Holdings \ Inc. \ and \ its \ subsidiaries. \ Unauthorized \ use, \ disclosure \ or \ reproduction \ is \ strictly \ prohibited.$ 

Version Date:

Palladio BiosciencesInsert Customer Name/Logo PK/PD STATISTICAL ANALYSIS PLAN: PROTOCOL PA-102 Page 27 of 39

PK Parameter	Definition	
	as (lixivaptan only):	
	
 
Day 1 AM: dose divided by AUC(0-inf), or
 
	
	
 
Day 7 AM: dose divided by AUC(0-last).
 
	
V z /F	Apparent volume of distribution following extravascular dosing (L), calculated as CL/F divided by $\lambda_Z$ (lixivaptan only).	

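### The three-quantifiable-sample minimum in PK/PD SAP 14.2 is not limited to AUC and lambda-z, so it can drop low first-dose metabolite profiles from the Cmax and tmax summaries

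*SAP*

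**What the plan says.** PK/PD SAP 14.2 introduces Table 3 as the set of parameters that "will be estimated for lixivaptan and lixivaptan metabolites by non-compartmental methods using validated software and actual elapsed time from dosing". The same paragraph ends with the entry rule: "A minimum of 3 quantifiable post-dose concentration-time data points will be required for calculation of PK parameters". It exempts no parameter.

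Table 3 lists Cmax and tmax for the AM and PM intervals of Day 1 and Day 7, each obtained "directly from the observed concentration versus time data". Lambda-z has its own minimum within Table 3: "A minimum of 3 data points will be used for determination". The general rule is therefore more than the lambda-z rule repeated.

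Four other provisions bear on the point:
- Section 14.2 opens with "Subjects with partial data will be evaluated on a case-by-case basis to determine if sufficient data are available". It does not say that this review overrides the minimum.
- Section 7.3 says "Missing data will not be imputed but analyzed as missing, except as specified in Section 14.2". The exceptions in 14.2 concern missing first-dose predose samples and BLQ values within a profile. None gives a Cmax to a profile below the minimum.
- Section 14.1, on concentration tables: "Plasma concentrations that are below the lower limit of quantification (BLQ) will be treated as zero for the computation of summary statistics". Low profiles stay in those tables.
- Section 7.2, Primary Estimand 2: "Population: ADPKD subjects with at least one post-dose PK assessment". It covers first and multiple doses, and its population is wider than the three-sample rule admits.

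**The concern.** Three points are needed for a terminal slope and are reasonable for an AUC. They are not needed to read a maximum and its time. When all samples are taken and most are BLQ, what fails the rule is low exposure itself, so exclusion depends on the quantity being summarised and the remaining geometric mean moves up.

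The likeliest place is a slowly formed metabolite after the first dose, where the early samples are the lowest. If exposure rises with dose, the 50 mg cohorts are more exposed to the problem than the 200 mg cohorts. Concentration tables (low profiles kept) and parameter tables (low profiles dropped) could then describe different subjects. Cohorts have 8 subjects, and PK/PD SAP 7.4 and 14.2 split them further by sex and by CKD1 versus CKD2. Section 6.1 needs three values for full descriptive statistics, so one lost profile can empty a small stratum.

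**Working it through.** **Inputs from the documents.** Eight subjects per cohort; CV 0.30 for lixivaptan Cmax (Protocol 7.4). Sampling from the Protocol Table 12-1 footnotes:
- Day 1 AM and Day 7 AM: 6 post-dose samples (1, 2, 4, 6, 9, 10 h).
- Day 1 PM: 5, counting the Day 2 predose sample at 14 h.
- Day 7 PM: 8 (1, 2, 4, 6, 14, 24, 48, 96 h).

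Protocol 3.1.1 equates 96 h with about 4 half-lives of the longest-lived metabolite, so that half-life is 96/4 = 24 h.

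**Plan's own figure.** Log variance = ln(1 + 0.30²) = 0.0862, so SD = 0.294. The 90% range is exp(±1.645 × √(0.0862/8)) = exp(±0.171) = 84.3% to 118.6%, as stated. This is the yardstick for the biases below.

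**What exclusion for lowness takes.** In a complete profile, 4 of 6 AM samples must be BLQ, or 3 of 5 on Day 1 PM, or 6 of 8 on Day 7 PM.

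**Effect of losing the lowest profiles.** Simulating 8 lognormal values with CV 0.30, the expected geometric mean is 106.2% of the true value if the lowest is dropped and 111.8% if the lowest two are. At an assumed CV of 0.60 these become 112.0% and 123.4%. A profile lost through missed samples unrelated to exposure gives 100.0%.

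**Lixivaptan, closed form.** Let r be the LLOQ divided by the median third-highest concentration, and assume concentrations proportional to Cmax. With c = ln(r)/SD, the share excluded is f = Φ(c), and geometric mean over truth is exp(SD × φ(c)/(1 − f)).
- r = 0.3: f = 0.00002, no bias.
- r = 0.5: c = −2.36, f = 0.9%, exp(0.294 × 0.0246/0.991) = 1.007, or +0.7%.
- r = 0.7: c = −1.21, f = 11.2%, exp(0.294 × 0.191/0.888) = 1.065, or +6.5%.

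Lixivaptan is materially affected only if the LLOQ exceeds about half the median third-highest concentration.

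**Metabolite, Day 1 AM, simulation.** The following are assumptions: parent absorption 0.5/h, parent half-life 6 h, metabolite half-life 24 h, lognormal between-subject CV of 30% or 60%, residual log SD 0.15. Median Cmax means the error-free value at 10 h. The model puts the six samples at about 5%, 15%, 41%, 66%, 93% and 100% of that value. The comparison is profiles with at least 3 quantifiable samples against profiles with at least 1.

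| CV | Median Cmax / LLOQ | Overstatement of geometric mean Cmax |
|---|---|---|
| 30% | 1.5 | 19% |
| 30% | 2 | 9% |
| 30% | 3 | 1% |
| 60% | 2 | 19% |
| 60% | 3 | 10% |
| 60% | 5 | 2% |

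At 30% CV the rule drops about 48%, 20% and 2% of detectable profiles. At 2 × LLOQ, the chance that a cohort of 8 loses at least one detectable profile is about 82% (30% CV) or 87% (60% CV). The effect is essentially gone by 5 × LLOQ (30% CV) or 8 × LLOQ (60% CV).

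**Dose.** Under assumed dose proportionality, a metabolite at 8 × LLOQ on 200 mg sits at 8 × 50/200 = 2 × LLOQ on 50 mg. The 50 mg figure would be affected and the 200 mg figure would not.

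**Day 7.** Superposing the doses in the same model, Day 7 PM levels from 1 to 24 h are 4.5 to 5.7 times the Day 1 AM Cmax. Even at 1.5 × LLOQ on Day 1 this is about 4.5 × 1.5 = 6.8 to 5.7 × 1.5 = 8.6 × LLOQ, so loss is negligible.

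**What keeping one-sample profiles leaves.** Against all profiles, those with at least 1 quantifiable value still overstate by about 5% (30% CV, 1.5 × LLOQ) and 11% (60% CV, 2 × LLOQ). Profiles with no quantifiable value need their own rule.

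**The case against.** The strongest reply is that no harm is shown. The LLOQ multiples, absorption rate, parent half-life and 60% CV are assumptions. The 30% CV is the plan's figure for lixivaptan, not a metabolite, and 24 h fits only the longest-lived metabolite. That stands: the plan may turn out to lose no profile at all.

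The consequences are also narrow. Metabolite Cmax from Day 1 AM enters no derived ratio: accumulation ratios are for lixivaptan only and metabolite-to-parent ratios are Day 7 PM only. The parameter-by-cohort scatter plots and the PK-PD plots are for lixivaptan only. A shortfall would show as n below N, and individual concentrations are listed on the Safety Analysis Set. This limits the damage, but n alone does not separate missed samples from low exposure.

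A reader might infer that the multiple-dose PK objective is compromised. It is essentially untouched, because accumulation lifts Day 7 levels well clear of the rule. A reader might also infer distorted renal-group contrasts. Nothing in the documents shows that at equal dose.

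Finally, for a rising metabolite a maximum resting on one or two late samples may be little more than the last value before the PM dose, so a reliability rule is defensible. But that argues for a flag: exclusion replaces imprecision with selection on exposure.

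**Conclusion.** The gap in the text is real: as written, the minimum governs Cmax and tmax, neither needs it, and no clause exempts them. If a fully sampled profile fails for lowness, geometric mean Cmax is biased upward.

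A reader might take the bias as established. The documents do not support that, since its size depends on an LLOQ, metabolite levels and a metabolite CV that they do not give. Under the assumptions shown, it ranges from nil to about 19%, against a planned upper precision limit of +18.6% for lixivaptan Cmax. It mainly concerns first-dose metabolite Cmax within Primary Estimand 2, more so at 50 mg if exposure rises with dose. This is a minor point, worth correcting because the correction is so cheap.

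**What to change.** In PK/PD SAP 14.2:
- Limit the three-sample minimum to AUC, lambda-z and parameters derived from them.
- Report Cmax and tmax whenever at least one post-dose sample is quantifiable, and flag in the listing any value resting on one or two samples.
- State that profiles with no quantifiable value are not in the geometric mean. Give the median as a summary that can include them.
- Show, by analyte, cohort and dosing interval, the number of profiles with no quantifiable value and the number excluded from each parameter.

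The cost is a few lines of SAP text and count rows in the table shells, with no new data. The downside is that a Cmax from one or two samples is less precise, which the flag makes visible.
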